At the second stage of preparation for the study to determine the accumulated absorbed dose in the lungs of a volunteer under internal irradiation of ^{99m}Tc after inhalation of UFCNPA, ^{99m}Tc obtained from the TechnegasPlus generator into the crucible of which an activity equal to 833MBq is loaded, a group of 5 volunteers without clinical and radiological signs of pneumonia will be preliminarily formed. For this purpose, at the initial stage, patients from this group will undergo: thermometry and physical examination, as well as X-ray CT of the thoracic organs. In addition, given the importance of immunological criteria in the pathogenesis of Covid-19, it is advisable to assess the immune status and the level of blood cytokines (pro-inflammatory cytokines: TNF α , IL-6, IL-12 TNF- α 4; anti-inflammatory cytokines IL-4, IL-10, TGF β).

In the absence of signs of pneumonia, patients in this group will undergo a single inhalation procedure, followed by a planar scintigraphy on a gamma camera at set intervals (see Item 7.3.2), and an assessment of the cytokine profile 3 hours after the procedure. The modes and geometry of measurements will strictly correspond to the modes and geometry of measurements on the phantom.

The study will enroll women and men aged 18 and over, hospitalized with a diagnosis of moderate new coronavirus infection (COVID-19) and receiving standard therapy.

Classification of COVID-19 by severity [11]:

Average, defined by the presence of at least one of the following signs:

- Fever above 38 ° C;
- NPV more than 22 / min;
- Shortness of breath during physical exertion;
- Pneumonia (susceptible to CT of the lungs);
- SpO2 <95%;
- CRP of blood serum more than 10 mg / l;

It is planned to include at least 10 patients in the protocol of a scientific prospective study.

All patients should undergo:

[figure not shown]
- laboratory test for confirmation of COVID-19 (PCR detection of SARS cov2 RNA);
- X-ray computed tomography of the thoracic organs, in which the presence of viral pneumonia is confirmed;
 - the levels of cytokines in blood plasma were determined (TNF α , IL-6, IL-12 TNF- α E, IL-4, IL-10, TGF β , interferon- γ -inducible protein (IP-10), monocyte chemoattractant protein 1 (MCP-1)
 - an assessment of the immune status was carried out,
 - biochemical indicators (levels of immunoglobulins and CEC) and indicators of the blood coagulation system (hemostasiogram) were evaluated;

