 - the levels of pathogen-specific immunoglobulins A, M, G were assessed (one of the factors in predicting the severity of the course of the disease);
 - output dosimetric control in accordance with the norms of NRB-99/2009 (SanPiN 2.6.1.2523-09).

Traditionally, in LDRT, the level of single doses with an anti-inflammatory effect ranges from 0.5 Gy to 1.0 Gy, and total doses - from 3 Gy to 6 Gy. With another method of dose administration, namely, by inhalation of UFCNPA, ^{99m}Tc, this range can be changed, therefore, the lower level is 10 cGy, and the upper one is 50 cGy.

Based on the dose coefficients, Table 1, presented in the ICRP Publication 128, in the lungs of a standard adult, in accordance with the standard kinetics model of the RFP UFCNPA, ^{99m}Tc, with inhalation of the drug activities of 833 MBq and 4165 MBq, average lung doses will be created internal irradiation equal to 0.1 Gy (10 cGy) and 0.5 Gy (50 cGy), respectively [12]. **Table 1.**

Age	Adult	15 years	10 years	5 years	1 year
Dose cGy / MBq	0,012	0,016	0,022	0,033	0,063

Radionuclide therapy will be carried out no later than one day after CT of the thoracic organs by inhalation of UFCNPA, ^{99m}Tc , carbon nanoparticles with ^{99m}Tc radionuclide attached to them (physical half-life 6.04 hours), by loading the TechnegasPlus 4165 MBq generator into the crucible.

Patients will be transported by specially designated ambulance vehicles using personal protective equipment (goggles, disposable gloves, FFP2 or FFP3 respirator, type 1 anti-plague suit, shoe covers) by the driver and accompanying medical worker. All transported persons are provided with a medical mask. After delivery, the vehicles are disinfected in a specially equipped place on the territory of a medical organization that receives COVID-19 patients (suspected).

Personal protective equipment (goggles, disposable gloves, respirator of the appropriate protection class, type 1 anti-plague suit, shoe covers) will also be used to protect personnel. At the end of the radionuclide therapy session, all surfaces in the room are treated with disinfectants with a virucidal effect, medical waste is collected in special containers for class B waste and disposed of, air disinfection is provided with bactericidal irradiators.

All work on packaging ^{99m}Tc , preparation of UFCNPA, ^{99m}Tc , inhalation of UFCNPA, ^{99m}Tc will be carried out in accordance with the norms of Radiation Standards-99/2009 (SanPiN 2.6.1.2523-09).

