7.3 Dosimetry

7.3.1. Measurements using a human phantom.

Measurements on a human phantom are carried out to obtain the coefficients of transition from the pulse count rate over the region of interest, obtained from planar scintigraphy in the "whole body" mode in the anterior and posterior direct projections (in imp./min), to the absolute activity of ^{99m}Tc in the region of interest (in kBq).

The measurements are made with the use of unified prefabricated human anthropometric phantoms UF-02T with different body manufactured by RADEK STC [15]. They are available at A. Tsyb MRRC.

Phantoms consist of rectangular polyethylene blocks weighing 1.0 kg and 0.5 kg. In the thoracic region of the phantom, there are phantoms of human lungs made of tissue-equivalent material with a density of 0.26 g / cm³ and a mass from 400 g to 1100 g, depending on the body weight of the phantom [16]. The phantoms of the lungs have through channels to accommodate sealed tubes with known ^{99m}Tc (kBq) activity, obtained from the ^{99m}Tc generator immediately before measurements. Measurements using planar scintigraphy with the following scanning parameters: low energy high resolution (LEHR) collimators, 140 keV photopeak (^{99m}Tc), discriminator window width $\pm 7.5\%$, tabletop speed 16 cm / min, matrix 256 \times 1024, are carried out and

recorded in strict compliance with the modes and geometry of measurements used in the corresponding measurements of patients and with the delineation of regions of interest.

According to the results of measurements on phantoms, the values of the transition coefficients from the counting rate of pulses in the region of interest (lungs) obtained from planar scintigraphy in the "whole body" mode in the anterior and posterior direct projections (in imp./min.) To the absolute activity of ^{99m}Tc in areas of interest (in kBq) - depending on the person's body weight. These coefficients are then used to determine the absolute activity of ^{99m}Tc in the lungs of patients with different body weights.

7.3.2 Determination of the accumulated absorbed dose in the lungs of volunteers under internal irradiation with ^{99m}Tc .

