After inhalation of UFCNPA, ^{99m}Tc , each volunteer undergoes planar scintigraphy in the "whole body" mode in the anterior and posterior direct projections with contouring of the areas of interest (lungs, whole body, abdominal region) and recording the results of measurements over the regions of interest with the following scanning parameters: low collimators energy high resolution (LEHR), photopeak 140 keV (^{99m}Tc), discriminator window width $\pm 7.5\%$, table deck speed 16 cm / min, matrix 256×1024 . Measurements are carried out and recorded in strict accordance with the modes and geometry of measurements used in the corresponding measurements of phantoms. The body weight, height and age of the volunteer are recorded. The activity of the RFP for inhalation, loaded into the crucible of the TechnegasPlus generator, equal to 833 MBq, is recorded. The time interval between the preparation of the RFP for inhalation and the beginning of inhalation, as well as the duration of inhalation and the number of breaths / exhalations, are recorded. The number of impulses recorded over the areas of interest is recorded. Scintigraphy is performed at the following times after inhalation: 10 minutes, 1 hour, 3 hours, 6 hours, 8 hours, 24 hours. The exact time and duration are recorded. Based on the results of scintigraphy, the functions of retention and removal of the drug from the areas of interest are described. The values of the measurement results, expressed in pulses above the zones of interest, are converted into activity values, expressed in kBq, using the coefficients of the transition from the pulse count rate over the region of interest to the absolute activity of ^{99m}Tc in the region of interest obtained from the data of phantom measurements (see clause 7.3. one). The time integrals of these functions are the values of the accumulated activity (kBq \times h). The calculation of the accumulated absorbed doses in the lungs and organs of a volunteer from internal irradiation of ^{99m}Tc is carried out according to the methodology of the Medical Internal Dose Committee [17], taking into account the results of measurements of the accumulated activity of ^{99m}Tc and using databases containing the values of the specific absorbed energy fractions of quantum and corpuscular energy calculated by the Monte Carlo method radiation in organs and tissues of a person of different sex and age [18-33].

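### The lung doses in Sections 6 and 7.3.2 are reference-lung values: 0.5 Gy is nominal for patients, and the volunteer doses take no account of each person's lung mass although chest CT is already required

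*Combined protocol and SAP*

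**What the plan says.** Section 6 (Research design) gives the range as two levels: "therefore, the lower level is 10 cGy, and the upper one is 50 cGy". It links them to activity through the dose-coefficient table in the same section (the second table numbered 1). The average lung dose is computed "in the lungs of a standard adult, in accordance with the standard kinetics model", "with inhalation of the drug activities of 833 MBq and 4165 MBq", and the result is "internal irradiation equal to 0.1 Gy (10 cGy) and 0.5 Gy (50 cGy), respectively". The table has a single adult coefficient, 0.012 cGy/MBq; its other columns are ages 15, 10, 5 and 1.

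Patients are adults of either sex ("The study will enroll women and men aged 18 and over"), and all are treated "by loading the TechnegasPlus 4165 MBq generator into the crucible". No adjustment for body or lung size is described. The five volunteers receive a smaller activity, also "loaded into the crucible of the TechnegasPlus generator, equal to 833 MBq, is recorded".

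Section 7.3.1 uses phantoms whose lungs have "a mass from 400 g to 1100 g, depending on the body weight of the phantom". Their purpose is to convert count rate to lung activity as a function of body weight. Section 7.3.2 then integrates each volunteer's lung activity over time and turns it into absorbed dose with databases of specific absorbed energy fractions, described as covering different sexes and ages (references 18-33). Weight, height and age are recorded; lung mass is not mentioned. Section 6 requires chest CT in the volunteers before inhalation, and in patients no more than a day before it.

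**The concern.** Absorbed dose is energy per unit mass, so the same activity gives a higher dose in a lighter lung. The plan knows that lungs differ, since its phantoms cover a wide range of lung mass, but it carries body size only as far as the activity. The last step, from activity to dose, uses reference-body values.

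Two results are affected. Task 2 is to determine the accumulated lung dose in volunteers. A reference-lung figure gives each person the wrong dose, and the spread across the five would reflect differences in uptake and retention but not in lung mass. For patients, the 0.5 Gy against which safety and laboratory findings will be read is an average for a standard body. With a planned minimum of 10 patients, one figure for all of them would hide real differences in exposure.

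**Working it through.** **Inputs from the documents.** Activities 833 and 4165 MBq; adult coefficient 0.012 and 15-year coefficient 0.016 cGy/MBq (Section 6); phantom lung masses 400 to 1100 g (Section 7.3.1).

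**Assumptions, because the documents give no figure.** Share of the load inhaled, f: 0.25 to 1. Reference lung mass, Mref: 800 to 1200 g. Individual lung mass, M: 700 g and 1100 g as illustrations. Dose proportional to 1/M, with M^(-2/3) as a weaker alternative.

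**1. The plan's own figures.** Dose = activity x coefficient.
- 833 x 0.012 = 9.996 cGy
- 4165 x 0.012 = 49.98 cGy

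Both stated levels reproduce. The upper level equals the standard-adult mean with no margin: rounding of the coefficient alone (0.0115 to 0.0125) gives 47.9 to 52.1 cGy.

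**2. Volunteers.** Lung activity is measured, so f drops out and lung mass remains. Actual dose / reference-lung dose = Mref / M.

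| Mref | M = 700 g | M = 1100 g | ratio |
|---|---|---|---|
| 800 g | 1.14 | 0.73 | 1.57 |
| 1000 g | 1.43 | 0.91 | 1.57 |
| 1200 g | 1.71 | 1.09 | 1.57 |

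The error for one person depends on Mref. The contrast between two people does not: 1100/700 = 1.57. With the weaker scaling it is (1100/700)^(2/3) = 1.35. The full phantom range gives 1100/400 = 2.75, but may include sizes below adult.

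**3. Patients.** Dose = 4165 x 0.012 x f x Mref/M, in cGy, with Mref = 1000 g. The 15-year column is 4165 x 0.016 x f.

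| f | standard adult | 15-year coefficient | 700 g | 1100 g |
|---|---|---|---|---|
| 1 | 50.0 | 66.6 | 71.4 | 45.4 |
| 0.5 | 25.0 | 33.3 | 35.7 | 22.7 |
| 0.25 | 12.5 | 16.7 | 17.9 | 11.4 |

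The 700 g to 1100 g contrast is 1.57 in every row. Whether anyone passes 50 cGy depends on f: it must exceed 50/66.64 = 0.75 on the 15-year coefficient, or 0.70 for a 700 g lung.

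**4. What is measured in patients.** Section 7.3.1 says the coefficients will serve to determine lung activity in patients. Section 7.3.2 describes timed scintigraphy and the dose calculation for volunteers only, and Table 2 in Section 9 schedules no scintigraphy. Section 6 also calls the volunteers patients in places, so the wording in 7.3.1 may refer to them.

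**The case against.** A reader might infer that the plan's own coefficients show small adults exceeding a 50 cGy ceiling. The documents do not support that, for three reasons.

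- The table has one adult coefficient. The other columns are ages that cannot be enrolled, so 66.6 cGy illustrates the effect of size and is not a plan figure for any patient.
- Nothing calls 50 cGy a per-patient limit. The two levels can be read as nominal values tied to the two activities, and Section 6 already describes them as averages for a standard adult.
- 4165 MBq is the crucible load. If half is inhaled, the standard adult is at 25.0 cGy and an assumed 700 g lung at 35.7 cGy, so the whole group could be below 50 cGy.

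All three stand. They rule out a claim of exceedance, but not the point about lung mass, because the relative difference between people is the same at every inhaled share.

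It can also be said that Section 7.3.2 records weight, height and age and cites databases by sex and age, so some matching to the person may be intended. That is fair, and we cannot see the databases. But sex and age define reference bodies, and no step brings in the individual's lung mass. Every listed entry in references 18-33 is also titled for an adult male. That repetition may be a copying error, but as written it provides neither a female nor an individual lung.

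**Conclusion.** The point holds in this form. For patients, 0.5 Gy is a nominal standard-adult mean; the individual dose may be higher or lower, and the documents do not allow the direction to be settled. For volunteers, the calculation as written yields a reference-lung dose, wrong by about Mref/M. At equal activity, 700 g and 1100 g lungs differ by 1.57-fold under 1/mass scaling and by 1.35-fold under the weaker scaling.

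This rests on reading Section 7.3.2 as using reference-body energy fractions without rescaling, and on illustrative lung masses. It does not depend on the inhaled share. It is a modest weakness with a cheap remedy, and bears most directly on Task 2.

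**What to change.** 1. **Section 7.3.2, volunteers.** Scale each volunteer's lung dose to that person's own lung mass, taken from the chest CT already required (segmented lung volume x CT density). State the reference mass behind the energy fractions and the scaling rule. List all five individual doses with their range. Cost: segmentation of about 5 existing scans, one line of calculation per person, and a dose that looks less exact. No new scan or visit.
2. **Sections 6, 7.3.1, 7.3.2 and 9.** Reconcile the text on three questions: whether 50 cGy is a limit or a nominal standard-adult mean; whether the coefficient applies to loaded or inhaled activity; and whether lung activity is measured in patients and, if so, when. Correct references 18-33 if the repeated entry is a copying error. Cost: wording only.
3. **Patient reporting.** Describe the patient dose as nominal. Report individual doses scaled by CT lung mass only if patient lung activity is measured. Without that measurement, CT mass gives relative values only, to be reported as such with the inhaled share stated as an assumption. Cost: segmentation of the patients' existing CT scans (at least 10). Imaging of lung activity would be extra if it is not already intended.

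No dose or clinical rule is proposed.

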7.1 Methodology for obtaining and introducing UFCNPA, ^{99m}Tc

It is necessary to connect an argon gas cylinder to the TechnegasPlus generator and open the gas cylinder, connect the TechnegasPlus generator to the mains, turn on the TechnegasPlus generator and open the drawer. Remove the charcoal crucible from its packaging and place it on a watch glass. Before adding sodium pertechnetate, ^{99m}Tc ($\text{Na}^{99m}\text{TcO}_4$), it is necessary to moisten the crucible using absolute or 95% ethyl alcohol,

then the moistened crucible must be placed in the contacts of the drawer section. Next, the crucible must be filled with sodium pertechnetate, ^{99m}Tc ($\text{Na}^{99m}\text{TcO}_4$) with a volume of 0.1 to 0.3 ml with the required specific activity and close the drawer section. Start a slow heating cycle at the end of which, if necessary, you can refill the crucible with sodium pertechnetate, ^{99m}Tc ($\text{Na}^{99m}\text{TcO}_4$) to increase the specific activity, and repeat the slow heating cycle. Upon reaching the required specific activity, start the firing cycle, which consists in a short-term increase in temperature to 2700 ° C in an argon atmosphere, after which UFCNPA, ^{99m}Tc is ready for use within 10 minutes. After that, it is necessary to close the gas cylinder and disconnect it from the TechnegasPlus generator, turn off the TechnegasPlus generator and disconnect it from the mains.

For best results, ^{99m}Tc -labeled carbon ultrafine aerosol must be administered to the patient as soon as possible after being generated, and certainly within the 10 minutes allowed. The ^{99m}Tc -labeled carbon ultrafine aerosol is introduced to the patient through a series of deep and slow breaths with a 5 second delay of each breath through a special system of tubes and filters with a check valve. Before and during the inhalation of the ^{99m}Tc -labeled carbon ultrafine aerosol, all patients and volunteers will be tested for the degree of blood oxygen saturation (pulse oximetry).

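### The 0.5 Gy lung dose applies a coefficient per MBq inhaled to the activity loaded into the crucible, so it is a nominal maximum, and no rule carries the volunteers' measured dose to the patients

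*Combined protocol and SAP*

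**What the plan says.** Section 6 sets the dose range for this route: "therefore, the lower level is 10 cGy, and the upper one is 50 cGy". It then applies the adult coefficient in its dose table, 0.012 cGy per MBq, to inhaled activities of 833 and 4165 MBq in a standard adult, and concludes that "average lung doses will be created internal irradiation equal to 0.1 Gy (10 cGy) and 0.5 Gy (50 cGy), respectively".

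The next paragraph describes treatment as given "by loading the TechnegasPlus 4165 MBq generator into the crucible". Read with Section 7.3.2, this means that 4165 MBq is put into the generator's crucible. For the preparatory stage, "a group of 5 volunteers without clinical and radiological signs of pneumonia will be preliminarily formed", with 833 MBq loaded. Section 7.3.2 uses one number for both quantities: "The activity of the RFP for inhalation, loaded into the crucible of the TechnegasPlus generator, equal to 833 MBq, is recorded".

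Section 7.3.2 also asks for inhalation details in volunteers: the delay from making the aerosol to the first breath, "as well as the duration of inhalation and the number of breaths / exhalations, are recorded". It schedules six scans, from 10 minutes to 24 hours, and a lung dose calculation.

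In Section 7.1 the aerosol is taken "through a series of deep and slow breaths with a 5 second delay of each breath", with pulse oximetry before and during inhalation in patients and volunteers alike. Section 6 lists an exit dosimetric control for all patients. Section 7.3.1 says that the phantom coefficients serve to find lung activity in patients of different body weights. Section 9 and its Table 2 contain no scan, lung dose or inhalation item.

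**The concern.** Activity loaded and activity inhaled are different quantities. Between crucible and lung lie the firing cycle, the tubes and filters, and the patient's own breathing. Section 3 itself names failures that could affect the yield of the aerosol. The plan makes no allowance for any loss, so a report quoting 0.5 Gy would give the top of the protocol's range as though it were the usual dose.

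Tasks 3 and 4 in Section 5 are to develop the method for patients and to assess whether it can be used. Both need an honest statement of the dose patients are likely to receive and of whether they managed the inhalation. The volunteers have no pneumonia, while Section 8.1 requires it of every patient, and SpO2 below 95% is one of six alternative signs of moderate disease in Section 6. Patients may therefore inhale differently from volunteers, and the readable text requires no record that would show it.

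**Working it through.** **Inputs**
- Coefficient: 0.012 cGy per MBq, adult (Section 6, dose table). That it is per MBq inhaled follows from the sentence that uses it; the cited source was not available.
- Loaded activity: 4165 MBq in patients (Section 6), 833 MBq in volunteers (Sections 6 and 7.3.2).
- Protocol range: 10 to 50 cGy (Section 6).
- Half-life 6.04 h (Section 6); aerosol to be used within 10 minutes (Section 7.1).
- Share *f* of loaded activity that is inhaled: not given. The values below are assumptions. Retention after inhalation is left out of *f* because the coefficient already rests on a standard kinetics model.

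**1. Reproduce the plan's figures.** 833 × 0.012 = 9.996 cGy and 4165 × 0.012 = 49.98 cGy. Both match the stated 10 and 50 cGy, with the loaded activity entered as if all of it were inhaled (*f* = 1).

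**2. Let the share vary.** Dose = loaded activity × *f* × 0.012, for a standard adult.

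| *f* (assumed) | Patients, 4165 MBq loaded (cGy) | Volunteers, 833 MBq loaded (cGy) |
|---|---|---|
| 1 | 49.98 | 10.00 |
| 0.5 | 24.99 | 5.00 |
| 0.2 | 10.00 | 2.00 |
| 0.1 | 5.00 | 1.00 |

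**3. Share at the lower level.** 10 / 49.98 = 0.20. Below this, the standard-adult dose is under 10 cGy.

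**4. What the volunteer stage can supply.** Expected patient dose = (volunteer lung dose / 833) × 4165 = 5.0 × volunteer lung dose. A measured volunteer dose under 2.0 cGy would thus imply an expected patient dose under 10 cGy, if patients inhale as volunteers do. This step needs no value for *f*, because the measured dose already reflects it.

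**5. Is decay the explanation?** Over 10 minutes the factor is 2^(−10 / (6.04 × 60)) = 0.981, a loss of 1.9%. Decay is not the issue.

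**6. Does Section 7.2 supply the share?** No. Its figure of more than 96% describes where the aerosol lies after inhalation has ended, not how much left the crucible and was inhaled.

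**7. What is specified for whom**

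| Item | Volunteers | Treated patients |
|---|---|---|
| Lung scans with times | Section 7.3.2 | None scheduled; ambiguous mention in Section 7.3.1 |
| Lung dose calculation | Section 7.3.2 | None specified |
| Interval, duration, breath count | Section 7.3.2 | None specified |
| Pulse oximetry at inhalation | Section 7.1 | Section 7.1 |
| Exit dosimetric control | Not stated | Section 6 |

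A figure next to the patient assessment list in Section 6 is not shown, so the patient column covers the readable text only.

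**The case against.** The plan can be defended on four grounds.

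*Patients may be measured after all.* Section 7.3.1 speaks of lung activity in patients. Section 7.1 names patients and volunteers separately, and Section 7.3.2 says volunteer throughout, so treated patients may well be meant. Against that, Section 6 also calls the volunteers patients, and the wording about matched geometry in Section 7.3.1 mirrors that in Section 7.3.2. The exit control applies to every patient, although it is listed under radiation-safety norms and not linked to lung dose. A reader might infer that a patient who inhaled little cannot be told from one who received the intended dose. The documents do not support that. They support only the narrower statement that verification in treated patients is neither scheduled nor specified.

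*The volunteer stage already measures the average relation of loaded activity to lung dose, and 0.5 Gy is presented as a model value.* Both are true. What is missing is the step that carries the measured relation to the patients' dose.

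*The shortfall is assumed.* This stands. No document supports any particular share, the 0.20 threshold simply restates 833/4165, and 10 to 50 cGy is not given as an acceptance limit for each patient. It would go too far to infer that patients will be under-dosed.

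*Difficulty with inhaling is conjecture.* Section 3 reports an average 8.5% fall in oxygen saturation during inhalation, but calls it transient, says the authors saw no apparent risk, and cites use in ventilated patients. Nothing in the documents links it to incomplete inhalation. Nor can breath count, duration and interval yield a lung dose. They are worth recording only as evidence of feasibility.

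**Conclusion.** The point holds, and its core is the dose statement. As derived in Section 6, 0.5 Gy is a nominal maximum for a standard adult who inhales all 4165 MBq loaded. The true figure could lie anywhere below it: 25 cGy if half is inhaled, 10 cGy at one fifth, 5 cGy at one tenth. These shares are illustrative, and the documents allow no single corrected dose. The expected dose can be estimated from the volunteer stage, on the assumption that patients inhale as volunteers do, but the plan does not say that this will be done. How far patients differ from volunteers cannot be judged from the documents.

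No planned test depends on this, and with no control arm described, better dose records would not establish cause. It remains worth correcting because dose and feasibility are central to Tasks 3 and 4 and the correction is cheap.

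**What to change.** 1. In Section 6, describe 0.5 Gy as a nominal maximum for a standard adult with all loaded activity inhaled. Before the first treatment, compute the expected patient dose as the volunteers' measured lung dose per MBq loaded × 4165 MBq, with the between-volunteer range. State whether it lies within 10 to 50 cGy. Report it in place of 0.5 Gy, noting that it assumes volunteer-like inhalation. Whether to change the loaded activity would be a separate decision.
2. In each treated patient, record the items that Section 7.3.2 already records in volunteers (interval from preparation to inhalation, duration, number of breaths) and whether the 5-second hold was achieved. List them per patient as a feasibility result for Tasks 3 and 4, not as a measure of dose.
3. In Section 7.3.1, say whether patients means treated patients. If so, give the scan time and report lung dose per patient.

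The cost is a few lines on the inhalation record, at a moment when staff already follow oxygen saturation, one clarification in Section 7.3.1, and a less favourable dose statement. No imaging, activity or visit is added unless Section 7.3.1 already intends patient scans.
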